### **General**

18. Subjects who have been placed in an institution on official or judicial orders.
19. Subjects who are related to or dependent on the Investigator, Sponsor, or study site such that a conflict of interest may arise.

#### **9.3.3 Strategies for Subject Recruitment and Retention**

Subject recruitment will be according to satisfaction of eligibility criteria at the end of parent study. The protocol requirements will be approved by an Independent Ethics Committee (IEC) or Institutional Review Board (IRB) prior to implementation.

Regular study monitoring will enable identification of any potential issues related to subject retention.

#### **9.3.4 Withdrawal of Subjects**

Subjects may voluntarily withdraw consent to participate in the long-term extension study for any reason at any time.

Withdrawal of consent occurs when a subject does not want to participate in the study anymore and does not want to attend any further visits or assessments, have further study -related contact, or allow analysis of already obtained biologic material.

If a subject withdraws consent, the Investigator must make every effort to determine the primary reason for this decision and record this information on the treatment disposition eCRF page. If the subject decides to completely withdraw from the study (refuses any further study participation or contact), all study participation for that subject will cease and data to be collected at subsequent visits will be considered missing. The IMP must be discontinued and no further assessments conducted. Further attempts to contact the subject are not allowed unless safety findings require communication or follow-up.

For safety reasons, and particularly following an AE, Week 208 (EoT/Follow-up) assessments should be conducted if the withdrawn subject is willing to undergo the assessments. Subjects who discontinue the study due to an AE considered related to study drug should be followed as described in [Section 12.1.1.1](#).

The appropriate personnel from the study site and designated CRO will assess whether IMP should be discontinued for any subject whose treatment code has been broken inadvertently.

The Investigator must also contact the IVRS to register the subject's discontinuation from IMP.

### **9.3.5      Investigational Medicinal Product Discontinuation**

Subjects may voluntarily discontinue IMP for any reason at any time, or completely withdraw from the study (see [Section 9.3.4](#)). Subjects who consent will undergo the EoT/Follow-up assessment approximately 4 weeks after administration of the last dose of IMP.

At any time during this long-term extension study, subjects not deriving sufficient clinical benefit in the opinion of the Investigator should be discontinued from IMP. Investigators should monitor the clinical benefit of each subject in an ongoing manner throughout the study in order to make the determination as to whether it is appropriate for them to continue to participate.

IMP must be discontinued under the following circumstances and further steps need to be discussed with the medical monitor:

- A serious adverse event (SAE), drug reaction or complication, or an unacceptable AE, whether attributed to IMP or not, that precludes continuation of treatment with IMP. This includes the development of allergic reactions or the development of other potentially serious drug reactions to medication required by the protocol,
- Diagnosis of malignancy (except basal or squamous cell carcinoma) during study (treatment may be continued at the discretion of the subject and Investigator, and in consultation with the medical monitor),
- Subjects who develop suicidal behavior ([Section 12.4](#)),
- Evidence of pregnancy,
- Withdrawal of informed consent,
- Lost to follow-up,
- Significant non-compliance of the subject with study procedures,
- Decision of the Sponsor to terminate the subject, site, or the study.

The derivation of clinical response (at Week 52 for the Phase 2 parent study) will be made within the IVRS system using information provided by the study site. The IVRS system will determine the subject's eligibility to continue into the long-term extension study. Subjects who fail to meet eligibility criteria at the end of their parent study will not be eligible to continue to the long-term extension study in accordance with the IVRS instruction, and would continue in the Follow-up period of their parent study.

## **Reasons for Temporary Discontinuation of Investigational Medicinal Product**

Investigational medicinal product may be temporarily suspended in the event of:

- Clinically important laboratory abnormalities,
- Subjects who develop suicidal ideation ([Section 12.4](#)),
- Other intercurrent illnesses or major surgery,
- Use of prohibited treatment (according to inclusion criteria of the parent study, [Section 9.3.1](#) and [Section 9.3.2](#)),
- Any other protocol deviation that results in a significant risk to the subject's safety,
- Sponsor decision.

After a laboratory abnormality leading to suspension of dosing normalizes sufficiently, IMP may resume at the discretion of the PI in consultation with the medical monitor. Similarly, IMP may resume after a prohibited medication leading to suspension of dosing is discontinued. A decision to discontinue IMP and/or to reinstitute IMP should be discussed with the medical monitor. The Investigator may suspend IMP at any time, even without consultation with the medical monitor if the urgency of the situation requires immediate action and if this is determined to be in the subject's best interest. However, the medical monitor should be contacted as soon as possible in any case of IMP discontinuation. Resumption of IMP after temporary discontinuation should always be discussed with the medical monitor.

### **9.3.6 Lost to Follow-Up**

All reasonable efforts must be made to locate subjects to determine and report their ongoing status. This includes follow-up with persons authorized by the subject. Lost to follow-up is defined by the inability to reach the subject after a minimum of 3 documented phone calls, faxes or emails (not performed on the same day), as well as a lack of response by the subject to a registered mail letter. All attempts should be documented in the subject's medical records. If it is determined that the subject has died, the study site will use permissible local methods to obtain the date and cause of death and as much other information as can be obtained, including post mortem reports.

Data to be collected at subsequent visits will be considered missing.

### **9.3.7 Discontinuation of Study Sites**

Study site participation may be discontinued if Sun Pharma Global FZE or designee, the Investigator or IRB/IEC of the study site judges it necessary for medical or safety reasons consistent with applicable laws, regulations and GCP. Sun Pharma Global FZE or designee may also discontinue the study site or study country should there be a change in the personnel (or structure) of the site or political (or economic) environment of the country such that

continuation of the study in the site or country may negatively impact the study or no longer serves the primary objective of the study.

### **9.3.8 Discontinuation of Study**

The study will be discontinued if Sun Pharma Global FZE or designee judges it necessary for medical, safety, or business reasons consistent with applicable laws, regulation and GCP.

## **10 TREATMENT OF SUBJECTS**

### **10.1 Identity of Investigational Medicinal product**

#### **10.1.1 Administration of Investigational Medicinal Product**

Investigational medicinal product will be supplied as [REDACTED] and administered SC. All subjects will be dosed at the same time points to maintain the study blind of the parent study where applicable (see [Section 10.2.4](#)). All subjects will be receiving tildrakizumab in accordance with their parent study dose regimen until at least Week 52 in the parent study and will transition to tildrakizumab 100 mg Q12 weeks thereafter there will be no placebo comparator group in this study.

If a subject misses a visit and/or a scheduled dose of IMP, the study site must reschedule a visit to ensure the dose of IMP is taken as soon as possible within the visit window. If after 2 attempts to reschedule or the visit window was missed and the subject still is not able to take the dose, the Sponsor should be contacted to determine if the subject should be discontinued from the study.

### **10.2 Investigational Medicinal Product Packaging and Labeling**

#### **10.2.1 Packaging**

Each [REDACTED] of IMP contains 1 mL of solution. A [REDACTED] of tildrakizumab contains 100 mg (100 mg/mL) of active drug.

#### **10.2.2 Labeling**

Medication labels will comply with the legal requirements of each country and be printed in the local language. They will supply no information about the subjects.

#### **10.2.3 Storage**

All drug supplies for this study must be stored under refrigerated conditions (2°C to 8°C) and according to labeled storage conditions. Until dispensed for administration to subjects, the IMP will be stored in a securely locked area, accessible to authorized personnel only. If a study nurse is selected to administer IMP in a home setting ([Section 9.1.3.3](#)), the study IMP should be stored and transported in accordance with the study recommendations. The IMP should not be stored at the subject's home and should accompany the study nurse on the day of the scheduled visit.

#### **10.2.4 Blinding and Randomization of Investigational Medicinal Product**

Subjects will be not be randomized and will enter the long-term extension study with one fixed dose regimen of tildrakizumab, 100 mg at Week 52 of the parent study. However, subject numbers based on allocation from an IVRS system will remain in place from the parent study until such time the blind is no longer required to be maintained.

A copy of the randomization code with true treatment allocations will be held by the designated CRO during the study. Another randomization list (containing kit number and treatment) will be provided to clinical supplies. The randomization codes associated with each subject will be disclosed to PK analysts who will keep PK results confidential until treatment completion of the parent study (for Phase 2 parent study, this will be following completion and database lock of all PsA subjects).

The long-term extension study is designed initially to maintain as last dosing regimen in the parent study followed by a regimen of 100 mg Q12 week, in an open-label fashion as blinding of IMP is no longer necessary to maintain. If a subject does not receive the scheduled dose, every effort should be made to administer the dose as soon as possible (see [Section 10.1.1](#)).

All safety assessments will be administered by the study coordinator or PI/designee.

Should a situation arise where unblinding is required, the Investigator at that study site may perform immediate unblinding via the IVRS without the need for communication with the Sponsor. This can only occur in emergency situations ([Section 10.3](#)).

At the time of the first IA for this extension study, the Phase 2 parent study will have been unblinded and hence no considerations of maintenance of blind will be necessary for those cohorts of subjects.

### **10.3 Procedure for Breaking the Randomization Code**

Subjects, study site personnel, persons performing the assessments, and data analysts will remain blind to the identity of the treatment from the time of randomization until such time the long-term study can become open-label for the relevant cohort of subjects ([Section 9.1.1](#)).

Emergency treatment code breaks should only be undertaken when it is essential to treat the subject safely and efficaciously. Most often, IMP discontinuation and knowledge of the possible treatment assignments are sufficient to treat a study subject who presents with an emergency condition. Emergency code breaks are performed using the IVRS. When the Investigator contacts the system to break a treatment code for a subject, he/she must provide the requested subject identifying information and confirm the necessity to break the treatment code for the subject. The Investigator will then receive details of the IMP for the specified subject and a fax or email confirming this information. The system will automatically inform the designated site monitor, medical monitor, and the project manager that the code has been broken, but no treatment assignment will be communicated.

It is the Investigator's responsibility to ensure that there is a procedure in place to allow access to the IVRS in case of emergency. The Investigator will inform the subject how to contact his/her backup in case of emergency when he/she is unavailable. The Investigator will provide the protocol number, IMP name if available, subject number, and instructions for contacting the local entity which has responsibility for emergency code breaks to the subject in case an

emergency treatment code break is required at a time when the Investigator and backup are unavailable.

#### **10.4 Subject Compliance**

The dosage, timing and mode of administration of IMP may not be changed. Any departures from the intended regimen must be recorded in the eCRF.

Investigational medicinal product accountability and subject compliance will be documented throughout the treatment period using study-specific IMP dispensing record forms. If a subject does not receive the scheduled dose, every effort should be made to administer the dose as soon as possible ([Section 10.1.1](#)).

Deviations from the intended regimen could occur due to:

- Receiving unscheduled IMP injections,
- Missing an injection,
- Receiving the incorrect IMP dose.

#### **10.5 Investigational Medicinal Product Accountability**

Records shall be maintained of the delivery of IMP to the study sites, the inventory at the study sites, the use of each subject and the return to the Sponsor.

These records shall include dates, quantities, batch numbers, expiry dates, and the unique code numbers assigned to the IMP and to the study subjects.

The Investigator shall be responsible for ensuring that the records adequately document that the subjects were provided the doses specified in the protocol and that all IMP received from the Sponsor is reconciled. All IMP must be returned to the Sponsor at the end of the study.

#### **10.6 Concomitant Therapy**

Subjects should abide by inclusion and exclusion restrictions for this long-term extension study.

Permitted medications include:

- Acetaminophen, except within 24 hours before a scheduled study efficacy evaluation,
- Non-steroidal anti-inflammatory drugs or low potency opioids (e.g., tramadol),
- Methotrexate or leflunomide,
- Oral corticosteroids (no more than daily 10 mg for maintenance dose),
- Non-drug therapy (including but not limited to physical therapy, massage, diet, exercise, emollients, and joint taping)..

Use of and adjustment of permitted medication is permitted throughout the study per Investigator discretion and therapeutic needs of the subject.

In accordance with the parent study, subjects are prohibited from use of the following at the time of written informed consent for and during the long-term extension study:

- High potency opioid analgesics (e.g., methadone, hydromorphone, or morphine) for the treatment of arthritis (allowed for treatment of other conditions for periods of up to 2 weeks),
- Sulfasalazine,
- Systemically administered calcineurin inhibitors (e.g., cyclosporine, tacrolimus),
- Azathioprine,
- Parenteral corticosteroids including intramuscular or intra-articular administration (topical, ophthalmic, intra-nasal, and inhaled corticosteroids are permitted) for the treatment of arthritis (allowed for treatment of other conditions for periods of up to 2 weeks),
- Live vaccines.

Any prohibited treatments must be discontinued prior to IMP initiation for the long-term extension study.

During this long-term extension study, subjects must not use systemic immunosuppressive therapies including commercially available or investigational therapies for PsO or PsA such as:

- Use of all anti-tumor necrosis factor agents, including etanercept,
- Use of B-cell and T-cell depleting/inhibiting agents,
- Use of any other commercially available or investigational biologic therapies (other than tildrakizumab) for PsO and/or PsA within 3 months or 5 half-lives (whichever is longer) prior to or during IMP in the long-term extension study,
- Use of apremilast, or other approved or investigational medications for the treatment of current condition which are not identified as permitted therapies,
- Use of secukinumab, ustekinumab, ixekizumab, brodalumab, or any drug targeting interleukin (IL) 17, IL 23, or the IL-12/IL-23-shared p40 molecule.

## **11 ASSESSMENT OF SAFETY**

The timing and frequency of safety assessments are described in [Section 9.1.2](#) and [Section 9.1.3](#).

### **11.1 Adverse Events**

The definitions for AEs and SAEs are provided in [Section 11.1.1](#). The PI is responsible for ensuring all personnel involved in the study are familiar with the content of this section.

#### **11.1.1 Definitions**

##### **11.1.1.1 Adverse Event**

An AE is defined as “any untoward medical occurrence in a subject, or clinical investigation subject administered a pharmaceutical product, and which does not necessarily have a causal relationship with this treatment. An AE can therefore be any unfavorable and unintended sign, symptom or disease temporally associated with the use of a medicinal (investigation) product, whether or not related to the medicinal (investigational) product”.

Any relevant observations made at the Baseline visit (including laboratory test results, and until the ICF is signed) are to be recorded on the AE eCRF, but will not be considered treatment-emergent AEs (TEAEs) for the long-term extension study, and will be reported separately from TEAEs. A TEAE includes any relevant observations following signing of the ICF for the long-term extension study, and will be recorded as an AE in the subject's AE eCRF; this includes physical examination findings, clinically relevant abnormal vital signs, clinically relevant laboratory abnormalities, and clinically relevant ECG findings. An AE relating to a pre-existing condition or ongoing at the start of the long-term extension study will only be recorded as a TEAE if there is a worsening of the pre-existing condition during the long-term study conduct with regard to nature, intensity or frequency.

An adverse drug reaction is an “untoward and unintended response to an IMP related to any dose administered”.

All AEs judged by either the reporting Investigator or the Sponsor as having a reasonable causal relationship to a medicinal product qualify as adverse drug reactions. The expression of “reasonable causal relationship” means to convey in general that there are facts or arguments which suggest a causal relationship. Subjects who discontinue the study due to an AE considered related to study drug should be followed until the event is resolved, considered stable, or the Investigator determines the event is no longer clinically significant.

##### **11.1.1.2 Serious Adverse Event**

An SAE is defined as, but is not limited to, an event that:

- Results in death,

Death is not an AE in itself, but an outcome. The cause of the death is the AE which resulted in death.

- Is life-threatening,

Life-threatening means that the subject was at immediate risk of death at the time of the SAE; it does not refer to an SAE that hypothetically might have caused death if it had been more severe.

- Requires in-patient hospitalization or prolongs existing hospitalization,

Hospitalization is defined as at least 1 overnight formal admission into hospital, usually in order to perform additional tests, provide treatment which it is not possible to provide at home and/or due to an unstable medical condition which requires specific monitoring of the subject. Pre-planned hospitalizations (known already prior to signing the ICF) will not be considered an SAE, unless any of the above criteria are fulfilled over the course of the hospitalization due to unplanned complications. "Social" hospitalization whereby it is administratively impossible to release the subject home is not necessarily an SAE. Complications that occur during hospitalizations are AEs unless they would qualify as an SAE for any of the above criteria. If the complication delays subject release from hospital then the AE becomes an SAE. Hospitalizations which are not performed due to an AE are not regarded as SAEs.

- Results in persistent or significant disability/incapacity,

The term significant disability refers to any condition that impairs physical/physiological well-being to the extent that the subject is unable to function normally. Physical disability may include, but is not limited to, permanent disability of locomotion or motility, but also systemic permanent dysfunction including heart failure, liver insufficiency or pulmonary fibrosis.

- Is a congenital anomaly/birth defect,
- Is an important medical event.

Important medical events that may not result in death, be life-threatening or require hospitalization may be considered as an SAE when, based on appropriate medical judgment, they may jeopardize the subject or the subject may require medical or surgical intervention to prevent one of the outcomes listed in this definition.

### **11.1.1.3 Adverse Events of Special Interest**

The events of severe infections (defined as any infection meeting the regulatory definition of a SAE or requiring intravenous antibiotics whether or not reported as a serious event), malignancies (including non-melanoma and melanoma skin cancer), confirmed Major Adverse Cardiovascular Events (MACE), and drug-related hypersensitivity reactions) will each be

identified a priori as an AE of special interest (AESI) for summarizing in this study. Major Adverse Cardiovascular Events include non-fatal stroke, non-fatal myocardial infarction, and cardiovascular death. All MACE events will be evaluated and adjudicated by a CAC ([Section 12.3.4](#)). An AESI must be reported as if it were an SAE ([Section 11.1.2](#))

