#### **9.3.2 Exclusion Criteria**

Subjects should be excluded from the study if they meet any of the following criteria:

1. New onset during the parent study of arthritic conditions other than the subject's original condition.
2. Female subjects of childbearing potential who do not agree to abstain from heterosexual activity or practice a dual method of contraception, for example, a combination of the following: (1) oral contraceptive, depo-progesterone, or intrauterine device; and (2) a barrier method (condom or diaphragm). Male subjects with female partners of childbearing potential who are not using birth control as described above must use a barrier method of contraception (e.g., condom) if not surgically sterile (i.e., vasectomy). Contraceptive methods must be practiced upon entering the study and through 16 weeks after the last dose

of IMP. If a subject discontinues prematurely, the contraceptive method must be practiced for 16 weeks following final administration of IMP.

3. Female is pregnant or breastfeeding, or planning to become pregnant or initiate breastfeeding while enrolled in the study or up to 16 weeks after the last dose of IMP.
4. Subject has previously been enrolled in this long-term extension study.
5. Any condition that in the opinion of the Investigator represents an obstacle for study conduct and/or represents a potential unacceptable risk for the subject.
6. Subject has an active infection or history of infections as follows:
  - a serious infection, defined as requiring hospitalization or intravenous anti-infectives within 8 weeks prior to the first IMP dose of the extension study, with the last dose having been received within 7 days of start of the extension study,
  - recurrent or chronic infections, e.g., chronic pyelonephritis, chronic osteomyelitis, bronchiectasis, or other active infection that, in the opinion of the Investigator, might cause this extension study to be detrimental to the subject.
7. Major chronic inflammatory or connective tissue disease other than PsA (e.g., rheumatoid arthritis, systemic lupus erythematosus, Lyme disease, or gout, Crohn's disease, etc).
8. Known diagnosis of fibromyalgia, regional pain syndromes or active uveitis/symptomatic inflammatory bowel disease requiring therapy.

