### 8.7.1 Adverse events

Any AE that started in the parent study must be reported on the medical history form in this extension study. Only those events that start on/after enrollment into the extension study or are ongoing at the start of the extension study and become worse after or concurrently to extension study enrollment must be reported as AEs.

All AEs will be classified by Primary System Organ Class (SOC) and Preferred Term (PT) according to the most recently available version of the MedDRA dictionary.

In summaries by SOC and PT, adverse events will be sorted within each SOC and PT in alphabetical order. In summaries by PT, AEs will be sorted within each PT in alphabetical order.

Details for imputing missing or partial start dates of adverse events are described in [Section 7.2.2](#).

TEAEs are defined as any AEs occurring or worsening on or after the date of signing of the Informed Consent Form for the extension study. AE summary tables will be presented for TEAEs only and will include the following:

- All TEAEs
- Related TEAEs (AE will be defined as related if causality is possibly, probably, or certainly related)
- TEAEs by maximum severity

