## **Adverse Events of Special Interest (AESIs)**

The events of severe infections, malignancies (including non-melanoma and melanoma skin cancer, excluding carcinoma in situ of the cervix), confirmed Major Adverse Cardiac Events (MACE), and drug-related hypersensitivity reactions will be identified a priori as AESIs for summarizing in this study. Severe infections are defined as any infection meeting the regulatory definition of a SAE, or any infection requiring IV antibiotics whether or not reported as a serious event, as per the regulatory definition. Major Adverse Cardiac Events include non-fatal stroke, non-fatal myocardial infarction and cardiovascular death. All MACE events will be evaluated and adjudicated by a Clinical Adjudication Committee. The AESIs will be summarized by SOC, PT and treatment group.

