# Statistical Analysis Plan (SAP)

laboratory results is to be reported as a non-serious AECI, using the terminology "accidental or intentional overdose without adverse effect."

2. An elevated AST or ALT laboratory value that is  $\geq 3 \times$  the ULN and an elevated total bilirubin laboratory value that is  $\geq 2 \times$  ULN and, at the same time, an alkaline phosphatase laboratory value that is  $< 2 \times$  ULN, as determined by way of protocol-specified laboratory testing or unscheduled laboratory testing, is to be reported as a non-serious AECI.
3. Infections that require IV antibiotics but do not meet the definition of an SAE will be designated a closely monitored AE for this study.
4. Depression and suicidal ideation and behavior events.

In addition, a listing containing individual subject adverse event data for TEAEs leading to discontinuation from study, Serious TEAEs, TEAEs leading to death, AESIs, and ECIs will be provided separately. All AEs, including pre- and post-treatment AEs, will be presented in an individual subject data listing.

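### The hypersensitivity AESI counts only reactions judged drug-related in an all-active study with no comparator, so an all-causality summary should stand beside it; the severe-infection wording has a minor mismatch

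*Protocol*

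**What the plan says.** **Hypersensitivity.** Protocol 11.1.1.3 names four AESIs: severe infections, malignancies, confirmed MACE and drug-related hypersensitivity reactions. The SAP repeats the restriction (8.7.1, AESI paragraph): "drug-related hypersensitivity reactions will be identified a priori as AESIs for summarizing in this study". An AESI carries the reporting duty of an SAE (Protocol 11.1.1.3 and 11.1.2) and gets its own summary by SOC, PT and treatment group (SAP 8.7.1).

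**Relatedness.** Protocol 11.1.1.9 gives the causality rating to the Investigator, on five levels from unrelated to certain. Protocol 11.1.1.1 lets either the Investigator's or the Sponsor's judgement qualify an event as an adverse drug reaction. For the related-TEAE table the SAP sets the cut: "AE will be defined as related if causality is possibly, probably, or certainly related". The AESI text in both documents says neither whose rating applies nor which levels count.

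**Severe infection.** In the Protocol an infection qualifies in one of two ways: by being an SAE, or by "requiring intravenous antibiotics whether or not reported as a serious event". The SAP's second route is "any infection requiring IV antibiotics whether or not reported as a serious event". Item 3 of the SAP's list of adverse events of clinical interest (AECIs) covers "Infections that require IV antibiotics but do not meet the definition of an SAE". At entry, exclusion criterion 6 (Protocol 9.3.2) uses a wider term: "a serious infection, defined as requiring hospitalization or intravenous anti-infectives within 8 weeks prior to the first IMP dose of the extension study".

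**Comparator.** The Protocol synopsis states that there is no placebo comparator; all subjects receive tildrakizumab.

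**The concern.** A count that requires a reaction to be drug-related mixes two things: how often the reaction occurs, and how often someone attributes it to the drug. In a controlled trial the second can be tested, because the same attribution habit applies to the control arm. Here there is no such arm. The SAP displays three tildrakizumab dose groups, which could show a dose contrast but no drug-free rate.

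The other three AESIs avoid this. Malignancy and severe infection carry no causality condition, and MACE is confirmed by an adjudication committee. Alternative explanations for a reaction will often be available, since NSAIDs, low-potency opioids, and methotrexate or leflunomide are permitted (Protocol 10.6), and the 'unlikely' category in 11.1.1.9 names concomitant drugs as one such explanation. Immunogenicity is part of the primary safety objective, and an unfiltered hypersensitivity count is the natural companion to the anti-drug antibody results.

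The infection point is smaller. The on-study term is narrower than the Protocol's own entry term, so one small class of infection could escape both special-interest categories.

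**Working it through.** The documents give no AESI rate, power or precision figure for this point, so there is nothing to reproduce. The check is a comparison of texts, followed by an illustration on stated assumptions.

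**1. What happens to a hypersensitivity reaction under each causality rating** (applying the SAP's related-TEAE cut to the AESI, which is an inference)

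| Rating | AESI summary | All-TEAE SOC/PT tables and listings | SAE report if serious |
|---|---|---|---|
| Unrelated, unlikely | no | yes | yes |
| Possibly, probably, certain | yes | yes | yes |

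The SAP already plans a table of related TEAEs, so related reactions are captured there as well. No output is specified that groups hypersensitivity terms regardless of cause. The SAP gives no term list for hypersensitivity, and the anaphylaxis criteria in Protocol 11.1.1.11, which span skin, respiratory, blood-pressure and gastrointestinal signs, are not linked to the AESI. Individual terms may therefore scatter over several SOCs.

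**2. Size of the dependence.** Let p be the share of reactions judged not related. Then all-causality count ÷ AESI count = 1/(1 − p). No document gives p; the range 0 to 0.5 is an assumption.

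- p = 0: 1/1.0 = 1.0
- p = 0.2: 1/0.8 = 1.25
- p = 0.5: 1/0.5 = 2.0

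**3. The same range as rates.** Inputs: up to 286 subjects (Protocol 9.1.1) and 208 weeks (SAP 3.3), with no dropout. Follow-up is at most 286 × 208 / 52.1775 = 1,140 subject-years. Assume 10 reactions in all, purely for illustration. The rate per 100 subject-years is 100 × k / 1,140, with an exact Poisson 95% interval.

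| Share judged not related | Events counted, k | Rate (95% CI) |
|---|---|---|
| 0% | 10 | 0.88 (0.42 to 1.61) |
| 20% | 8 | 0.70 (0.30 to 1.38) |
| 50% | 5 | 0.44 (0.14 to 1.02) |

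The intervals reflect sampling error only. The movement down the table comes from attribution in the same subjects, and no interval covers it.

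**4. Which infections are missed.** Protocol, SAP and AECI item 3 agree with each other on antibiotics; exclusion 6 says anti-infectives. An infection falls in the gap only if all of these hold: it was treated with an IV antiviral or antifungal; it received no IV antibiotic; it met no listed seriousness criterion such as hospitalization; and it was not judged an important medical event under Protocol 11.1.1.2. The documents support no estimate of how many there would be, and zero is possible.

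**The case against.** The strongest reply is that both definitions do what they declare. The stated targets are severe infections and drug-related reactions, so leaving out ordinary non-serious infections, or reactions attributed elsewhere, is their scope. A reader might infer that the definitions discard the very events they are meant to catch. The documents do not support that reading, and for infections only the antibiotic/anti-infective gap remains.

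A reader might also infer that filtered reactions vanish. They do not. All AEs go to the Sponsor whatever their cause (Protocol 11.1.1.8), SAEs are reported within 24 hours regardless of causality (11.1.2), and all TEAEs are tabulated by SOC and PT and listed (SAP 8.7.1). What is lost is AESI status: the dedicated summary and, for non-serious events, expedited reporting. It is fair to say that an all-causality count could be assembled from the planned tables. But without a fixed term list the choice of terms would be made after the data are seen. Table templates sit in a separate document (SAP section 9) and might contain such a grouping.

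Two further readings go too far. One is that the Investigator alone decides: the AESI text names no judge, and Protocol 11.1.1.1 also admits the Sponsor for adverse drug reactions. Moreover, if the SAP's cut applies, 'possibly' counts as related, so the threshold is low. The other is that a known undercount exists: no document supports any particular share judged unrelated, and the ratio compares two different quantities rather than showing an error in the AESI as defined.

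On infections, it is also true that an eligibility criterion and a reporting category need not match, and that the important-medical-event route will recover some cases.

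**Conclusion.** The point holds as a modest improvement to the analysis plan. The hypersensitivity AESI count rests on causality ratings that cannot be checked in a study without a comparator, and no all-causality grouping is specified beside it. The size is unknown. On the assumption that 0% to 50% of reactions are judged not related, the all-causality count is 1.0 to 2.0 times the AESI count; the rates shown also assume 10 reactions and complete follow-up of 286 subjects. The data are collected either way, so what is at risk is how the signal is summarized.

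The infection wording is a secondary and minor inconsistency, confined to non-serious infections treated with IV antivirals or antifungals.

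**What to change.** 1. **SAP 8.7.1, hypersensitivity.** Add one summary of all hypersensitivity TEAEs, regardless of causality, from a PT list fixed before the analysis. Show the drug-related events as a sub-row. State whose rating defines that sub-row and that the related-TEAE cut applies to it. This uses AE data already collected and needs no Protocol change.
2. **Infection wording.** Reconcile the term in Protocol 11.1.1.3, the SAP AESI paragraph and AECI item 3 with that in exclusion criterion 6. The SAP summary can use the broader term now, identifying cases from recorded concomitant medications, provided that route and indication are captured (the documents do not show this). The Protocol wording affects expedited reporting and ethics approval, so it can follow at the next amendment.

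The cost is one term list, one extra table and small wording edits. The downside for the Sponsor is slightly less favourable counts; the drug-related count stays visible.
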